### 5.4.3 Prior and Concomitant Diseases

Relevant additional diseases present at the time of informed consent are regarded as concomitant diseases and will be documented on the appropriate pages of the case report form (CRF). Included are conditions that are seasonal, cyclic, or intermittent (e.g. seasonal allergies; intermittent headache).

Abnormalities which appear for the first time or worsen (intensity, frequency) during the trial are adverse events (AEs) and must be documented on the appropriate pages of the CRF.

#### 5.4.4 Prior and Concomitant Medication

The treatment of accompanying illnesses not subject to the exclusion criteria is permissible if this is not expected to have any effect on the outcome measures used in this study and to interfere with the trial medication.

In particular, the following drug groups are **not permitted** as concomitant medication:

- Concomitant treatment with Vitamin-K antagonists or DOACs
- Platelet-inhibitors, if it is perceived that the potential benefit of this combination does not outweigh the risk of complications (for example: caution with combination of ASA with clopidogrel, while combination of ASA with dipyridamole is permitted)

The following drug groups are **permitted under restriction** as concomitant medication:

- Acetylsalicylic acid for other indications (e.g. short term use for a migraine attack).

If concomitant drugs are administered, these must be recorded in the patient file and in the CRF, stating

- The type (preferably the generic name / INN, or trade name)
- The route of administration
- The regimen including: dosage schedule, daily dose (if not indicated by the type), and form of application
- The indication
- The duration

Existing, permitted concomitant treatments are not to be changed during the course of this study.

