### 2.2 Secondary Objectives and Secondary Endpoints

Secondary objectives of the study are:

- A) To assess whether ASA reduces the risk of aneurysm rupture or growth compared with no ASA treatment.
- B) To assess whether intensive blood pressure lowering therapy reduces the risk of aneurysm rupture or growth compared with no intensive blood pressure lowering therapy.

- C) To assess whether intensive blood pressure treatment plus ASA reduces the incidence of cardiovascular events compared with standard BP treatment alone.
- D) To assess whether beneficial effects of the intervention with intensive blood pressure treatment and ASA are not negated by side effects of the intervention.
- E) To assess the effect of the intervention on quality of life
- F) To investigate if the intervention is cost-effective

Secondary endpoints of the study are:

1. Any growth or rupture of aneurysm during follow-up irrespective of the duration of trial participation
2. Difference of aneurysm volume (defined as increase of aneurysm volume in computerized measurements from source images by >10% and >3mm^3) or aneurysm shape (e.g. development of daughter sac)
3. Development of de novo aneurysm on serial imaging
4. If a second aneurysm is present: Growth in diameter or volume and alteration of shape of this second aneurysm.
5. Clipping/coiling during the study period
6. Any ischemic or haemorrhagic stroke, defined as clinical symptoms of stroke AND a compatible lesion on imaging
7. Myocardial infarction defined as increase of Troponin, CKMB and/or presence of new significant Q waves obtained in ECG
8. Vascular death (including fatal stroke, fatal myocardial infarction, sudden death)
9. Death from all other causes
10. Major spontaneous bleeding requiring hospitalisation defined as substantially disabling bleeding, intraocular bleeding leading to the loss of vision, or bleeding necessitating the transfusion of at least 2 units of erythrocyte concentrates
11. Blood pressure; any data on blood pressure management used
12. Safety aspects (adverse and serious adverse events, including those mentioned above, see also 8.1.6 and 8.2)
13. Quality of life (as determined by completion of the paper-based EQ-5D-5L form by patient)

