### 3 TRIAL DESIGN AND DESCRIPTION

#### 3.1 Trial design and justification of design aspects

This phase III multicenter, randomised, controlled trial with a PROBE design (prospective, randomised, open-label trial with blinded outcome assessment) is designed to assess whether a strategy with low dose ASA (81 mg/ day - 100mg/day) and intensive blood pressure treatment (targeted systolic blood pressure below 120mmHg) with weekly measurements using a home blood pressure measuring device reduces the risk of intracranial aneurysm rupture or growth, which is an established surrogate for the risk of rupture, compared with standard care (i.e. no ASA and blood pressure management according guidelines, which usually advise treatment if systolic blood pressure exceeds 140mmHg).

We will perform a phase III trial instead of a phase I/II trial since the protective effect of ASA on aneurysm inflammation or rupture was highlighted in a nested case-control study of UIA patients (n=1691) as well as in a small phase I trial randomising patients to ASA treatment or treatment as usual, which showed a significant reduction of radiological and histological aneurysm wall inflammation as surrogates for rupture. Further, the recent SPRINT study randomising 9361 patients to intensive versus standard BP treatment demonstrated a reduction of the primary composite outcome (myocardial infarction, other acute coronary syndromes, stroke, heart failure, or death from cardiovascular causes) without affecting the overall incidence of adverse or serious adverse events.

We chose an open-label design with observer-blinded outcome adjudication (by two independent neuroradiologists), because: a) a double or single-blinded study with predefined blood pressure targets would not be feasible, irrespective of the concomitant ASA treatment, b) to allow inclusion of UIA patients who are already treated for hypertension; and c) for pragmatic reasons, e.g. to not having to unblind treatment allocation for patients, who require a medical procedure potentially under ASA during the duration of the study (for at least 36±6 months after randomization). Also, due to very specific and well-known effects of ASA, it would be very likely to un-blind the patient by side effects.

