Because the 5-year risk of rupture is usually <3% in patients with small aneurysms, a randomized trial with rupture as the main primary outcome measure is unfeasible. We therefore combine aneurysm rupture with aneurysm growth as the primary outcome measurement, since UIA growth occurs more often and is a predictor of aneurysm rupture (see also above). The risk of growth is approximately 15% in 3 years, and approximately 18% in 5 years.

From a scientific perspective it would be important to understand the individual protective effects of both factors, i.e. intensive blood pressure reduction and ASA treatment, on aneurysm growth or rupture. We decided on a two-arm trial (i.e. concomitant ASA treatment plus intensive blood pressure treatment) instead of a three-arm trial (i.e. ASA treatment or intensive blood pressure management or standard of care), because in a three-arm trial investigating the protective effect of each component separately, the effect size for each treatment component would be smaller than for the combined effect. Hereby, the number of patients would not only increase as a result of adding an additional arm, but also because the effect size for each component was smaller.

We assume that combined ASA and intensive blood pressure lowering will reduce 3-year incidence of the primary outcome (aneurysm rupture or growth) from 15% to 8.25%, thus a relative risk reduction of 45%. We previously considered a trial with ASA only (without blood pressure reduction). For such a trial we assumed that the risk reduction to be attributed to ASA is 22.5%. Then the reduction by ASA monotherapy would be from 15% to 11.625% and the subsequent number for the a trial with two arms and with such a contrast would be 2 x 1597 for a total of 3194 patients who are available for the analysis. Even if we assume that the risk reduction contributed

|   |   |                               |
|---|---|-------------------------------|
| Clinical Trial Code: Protect-U
EudraCT: 2017-000514-35 | Trial Protocol
Version 07 - August 23 - 2022 | Page 26 of 62
CONFIDENTIAL |
|---|---|-------------------------------|

to ASA would be as large as 30% (15% down to 10.5%) a two-armed trial would require 2 x 864 = 1728 patients. Based on these calculations we decided against such a design.

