## 5 INVESTIGATIONAL MEDICINAL PRODUCT (IMP)

### 5.1 Study medication

#### 5.1.1 General Information

The sponsor (UMM) will provide the quantity of trial medication required for the clinical trial sites in Germany and the Netherlands.

Supply of IMP in additional countries will be managed by the national coordinators in accordance with the national regulations.

The medication provided must be used only in the context of this clinical trial. Careful records will be kept of the trial medication supplied to the centres and distributed to the patients. If deficiencies of the trial medication are noticed, the monitor and the project manager must be informed immediately.

Blood pressure lowering drugs will not be part of the IMP. The general practitioner will control the blood pressure target and prescribe blood pressure lowering drugs. The general practitioner can decide himself/herself on the type of antihypertensive drug(s) he/she wants to use to decrease the blood pressure.

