- Patients in the intervention arm will be provided with a letter to the treating physician explaining the study in detail and the blood pressure limits aimed for (120 mmHg systolic). Also a device for blood pressure measurements at home will be handed to the patient. The patient will be explained how to do measurements with this device. Patients provided with an electronic blood pressure measuring device are recommended to use this device to measure blood pressure at home at least once per week and up to 4 times per week, which will ensure that we do not exceed the maximum of 100 measurements at the time of each follow-up. However, if a patient would not do weekly measurements, this would not be defined as protocol deviation.

|   |   |                               |
|---|---|-------------------------------|
| Clinical Trial Code: Protect-U
EudraCT: 2017-000514-35 | Trial Protocol
Version 07 - August 23 - 2022 | Page 36 of 62
CONFIDENTIAL |
|---|---|-------------------------------|

The last routine imaging of the aneurysm (either CTA or MRA) within 3 months before randomization) will be uploaded to a central server in a pseudonymised manner by using the patient ID number and date of imaging. The pseudonymisation method must not reveal the allocation to intervention group or standard of care, to permit a blinded imaging assessment. Screening and Baseline visit may be performed at one single day.

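### Section 5.4.4 forbids changing existing permitted treatments and does not exempt antihypertensives, which the trial needs to be adjustable in both arms

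*Protocol*

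**What the plan says.** Section 5.4.4 (Prior and Concomitant Medication) names the drug groups that are barred (anticoagulants, some platelet inhibitors) or restricted (ASA for other indications). It then says what must be recorded, and closes with "Existing, permitted concomitant treatments are not to be changed during the course of this study". Antihypertensives appear nowhere in the section, and no other section takes them out of the rule.

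Other sections depend on these drugs being adjustable:

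- **3.1** gives as one reason for the open-label design "to allow inclusion of UIA patients who are already treated for hypertension".
- **5.1.1** says "Blood pressure lowering drugs will not be part of the IMP", and leaves their prescription to the family doctor: "The general practitioner will control the blood pressure target and prescribe blood pressure lowering drugs".
- **6.2** adds that anyone allocated to the intensive strategy "will be provided with a letter to the treating physician explaining the study in detail and the blood pressure limits aimed for".
- **6.3** has the investigator review the home readings and decide whether the GP should improve the patient's blood-pressure treatment.
- **1.3** lets the treating physician adjust some blood-pressure drugs when side effects occur. **4.6.1** lets the component responsible for severe side effects be adjusted or stopped while the other continues.
- **2.1** defines the comparator as blood-pressure management under guidelines, which usually advise treatment above 140 mmHg systolic.

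**The concern.** A patient who enters on an antihypertensive has an existing concomitant treatment that is not IMP. On its face the closing sentence of 5.4.4 applies to that drug and forbids any change to it for the length of the study, at least 36 months and at most 120. The trial's own procedures call for such changes: upward to reach the intensive target, downward for hypotension, and in either direction under guidelines in the control arm.

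Two things are at stake, both limited. Sites and monitors could differ on whether a dose change is a protocol deviation. And a site that took the sentence at its word would hold back titration, reducing the blood-pressure contrast among its patients, or delay a dose reduction that safety requires.

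**Working it through.** No arithmetic applies, because the point rests on no figure. The check is to apply the sentence to each kind of patient the protocol expects.

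1. **Intervention arm, already on an antihypertensive, above target.** Take 135 mmHg on one drug, as an illustration. The target is under 120 mmHg. Section 6.3 leads to a GP referral, and the ordinary next step is a higher dose, a switch or an added drug. A higher dose or a switch changes an existing treatment, so 5.4.4 forbids it. Whether adding a drug counts as a change is unclear. *Conflict with 6.3.*

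2. **Intervention arm, already on an antihypertensive, severe orthostatic hypotension.** Sections 1.3 and 4.6.1 allow the drug to be reduced or stopped. Section 5.4.4 does not. *Conflict, and on the safety side.*

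3. **Intervention arm, no antihypertensive at entry.** A newly prescribed drug is not an existing treatment at entry. GP prescribing under 5.1.1 and the target letter under 6.2 therefore do not in themselves conflict with the sentence. *No conflict.*

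4. **Control arm, already on an antihypertensive, pressure above the guideline threshold.** Guideline care, which defines this arm in 2.1, may call for a change. Section 5.4.4 forbids it. *Conflict with 2.1.*

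Is there an exemption elsewhere? Section 5.1.1 does not supply one: by keeping the drugs out of the IMP it leaves them outside the trial-medication rules. Section 5.4.3 treats relevant diseases present at consent as concomitant diseases. Pre-existing hypertension fits that description, so its treatment would naturally be read as concomitant medication.

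Does the deviation table in 4.6.1 settle how a change is classed? It mentions visit timing, missing samples and missing examinations, but not medication changes. Section 6.2 does state that skipped weekly home readings are not a deviation. Nothing comparable is said about titration.

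Could the classification reach the primary result? Section 9.2 analyses all randomised patients as randomised, with a narrow exception for ineligibility discovered later. Section 9.3 has a committee grade deviations as major or minor by consensus. A dose change logged as a deviation would not by itself remove a patient from the primary analysis.

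**The case against.** The best reply is that blood-pressure drugs in the intervention arm are not concomitant treatment at all. Section 4.6.1 speaks of two components of the intervention, blood-pressure control and ASA, and section 5.5.1 makes intensive blood-pressure treatment part of the allocated arm. Section 5.4.4 opens on accompanying illnesses, and a randomised component is not naturally one of those. The specific instructions would normally override a general closing sentence. Moreover, the GP, not the site, writes the prescriptions, and has been told the target.

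Much of this stands. It makes it likely that sites titrate anyway, and it is why the point is minor. But the protocol nowhere states the exemption, and the reply does not reach controls, whose antihypertensives belong to no experimental component yet may need changing.

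Two stronger readings are tempting and are not supported.

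- A reader might infer that 5.4.4 bans antihypertensives outright, because treatment of accompanying illness is "permissible if this is not expected to have any effect on the outcome measures used in this study", blood pressure is a secondary endpoint ("Blood pressure; any data on blood pressure management used"), and lowering it is expected to reduce the primary outcome ("We assume that combined ASA and intensive blood pressure lowering will reduce 3-year incidence of the primary outcome"). That strains the text. It treats a randomised component as an accompanying illness, and the list of barred drugs that follows does not include antihypertensives.
- A reader might infer a loss of power, as if only ASA would act. With 353 per group and 15% in controls, the ASA-alone effects considered in 3.1 would give about 26% power (22.5% risk reduction) or 43% (30%). These figures assume that blood-pressure treatment helps nobody. The sentence leaves new prescriptions untouched, and nothing suggests that sites would follow it throughout. They are not a consequence of this finding.

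**Conclusion.** The closing sentence of 5.4.4 is wrong as written. It has no exemption for antihypertensives and, read literally, contradicts 3.1, 6.3, 1.3, 4.6.1 and 2.1. The severity is minor. The practical effect is confined to uneven handling of titration as a deviation and to any site that obeys the sentence. Neither is shown to be likely.

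No sample size, power or analysis figure changes, and the intention-to-treat analysis stands. The number of patients exposed to the conflict cannot be calculated, because the protocol gives no share on antihypertensives at entry. The conclusion assumes only that a non-IMP drug taken before enrolment counts as existing concomitant treatment, which is the ordinary reading and is not displaced anywhere in the protocol.

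**What to change.** Add one sentence after the closing sentence of 5.4.4:

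> Blood-pressure-lowering drugs are exempt from this rule in both arms: they may be started, adjusted or stopped to reach the assigned target (intervention), according to guidelines (control), or for side effects; changes are recorded as concomitant medication and are not protocol deviations.

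This can go into the next amendment, with a short note to sites and monitors. It needs no extra patients, visits or procedures, and no change to the analysis.

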#### 5.4.5 Adjustments to dosage of the IMP in the individual trial subject

- A) The use of ASA may be interrupted, if a patient needs surgery during the course of the clinical trial. It will be resumed as soon as possible after surgery.
- B) No changes in IMP dosage are intended or permitted, even in case patients require a higher dose of ASA for other indications. However, if patients are medically required to be treated with higher doses of ASA (e.g. due to cardiovascular event) while being on treatment with the IMP, the treating physician can prescribe ASA as required and the IMP will be stopped for the time in which ASA is prescribed.
- C) For safety data, patients of the intervention group, who received concomitant long-term ASA will be analysed as per protocol, patients of the control group as ITT.

No further adjustments are planned.

## 5.5 Randomisation

### 5.5.1 Randomisation method

For randomisation an online tool (<https://www.randomizer.at/>) will be used. Any patient included will be 1:1 randomised into one of the two study arms: 1) a strategy with ASA 81 - 100mg/day and intensive blood pressure treatment (targeted systolic blood pressure below 120mmHg) with weekly measurements using a home blood pressure measuring device; or 2) standard of care.

There is no placebo group. Each study centre will be provided with an access code to perform the randomisation independently. Stratification will occur according to centre.

## 5.6 Blinding

This is an open trial, in which patients and investigators are not blinded. However, there will be an examiner-blinded assessment of images, therefore no information of patient allocation using patient ID-numbers or other data that would unblind the allocation of a patient to one of the two trial arms should be made available prior to the imaging analysis.

## 6 DESCRIPTION OF TRIAL VISITS

The study period for an individual patient consists of a minimum treatment period of 36 months and a maximum treatment period of 120 months (all patients stay on intervention until 3 years of the last patients' enrolment, even if the primary endpoint has occurred for the purpose of the secondary endpoint analyses).

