## 4.6 Criteria for Withdrawal

### 4.6.1 Withdrawal of Patients from Treatment

Any patient can withdraw from the treatment at any time without personal disadvantages and without having to give a reason. Patients who discontinue participation in the clinical study on their own or patients who are withdrawn by the investigator, for reasons other than disease progression (i.e. in case of AEs, protocol violations), will be defined as premature withdrawals. Withdrawn patients will be asked to attend a final follow-up visit and to return unused trial medication. Premature withdrawals will not be replaced. The time of treatment discontinuation must be documented in the patient file and on the CRF.

The investigator can also discontinue the participation of a patient in the study after considering the risk-to-benefit ratio, if he/she no longer considers the further treatment of the patient according to study protocol justifiable. The date of and the primary reason for the withdrawal, as well as the observations available at the time of withdrawal, are to be documented on the CRF. Reasons leading to the withdrawal of a patient can include the following (**one primary reason must be determined**):

- **Lack of efficacy** of the experimental intervention
- **Intolerable adverse events** from **both** components of the intervention (intensive blood pressure control **and** ASA-medication), e.g.
  - Any bleeding that results in hospital inpatient treatment
  - Severe skin reaction and/or asthma requiring treatment with medication exceeding a single dose
  - Gastric ulcer, if not possible to manage by gastroprotective co-medication
  - Severe orthostatic hypotension
- Disease progression
  - In patients with 1 intracranial aneurysm, end of treatment applies if aneurysm rupture (SAH) occurs or interventional treatment of the aneurysm (endovascular or neurosurgical). Patients who have multiple aneurysms can stay in the trial if growth, rupture or preventive treatment of 1 aneurysm occurs
- **Lack of patient's cooperation**, e.g.
  - Patient's request to withdraw
  - Lack of compliance, patient fails to attend the interim visits as agreed or perform self-medication according to schedule
- **Other reasons** (noting reason), e.g.
  - Other diagnosis than study disease
  - Did not meet major in-/exclusion criteria (coming to light after randomisation)

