- Existing or intended pregnancy, lactation in patients of the intervention group. If patients in the control group become subsequently pregnant and/or need to breastfeed after randomisation, they will not be excluded from the trial.

All patients who finish the study prematurely will be asked to attend a follow-up visit and to return unused trial medication. The patient must be asked to consent to this last examination. The withdrawal examination will be documented in the CRF.

If a patient does not come to a visit, the patient will be contacted and asked for information. If the patient wants to withdraw and agrees to give explaining reasons, the reason should be documented in the patients file and in the CRF.

In case of early withdrawal, the last aneurysm imaging will be used for the primary outcome analysis (*last observation carried forward*).

If a patient has severe side effects from one component of the intervention only, (e.g. severe orthostatic hypotension from intensive blood pressure control or major gastrointestinal bleeding from ASA), it can be decided to adjust or stop the component of the intervention causing the side effects, while continuing the other component of the intervention.

For documentation of AEs and SAEs see 8.1.6 and 8.2.

| Term                         | Definition   | Comment/ Sample  |
|------------------------------|--|--|
| Drop-out, study              | 
Participation terminated completely, including follow-up
 
Possible reasons:
 
 
• Patient withdraws consent: Withdrawal
 
• Patient moved/cannot be contacted
 
• Interventions cannot be performed due to medical reasons
 
• Non-compliance of patient
 
 
Drop-out after completion of study intervention:
Lost to follow-up
 
Final examination will be performed, if patient agrees. Study-Completion/ Withdrawal-form will be completed.
 | 
ITT-sample
 
ITT-sample (if study intervention completed)
  |
| Drop-out, study intervention | Termination of study intervention, follow-up once as per protocol.   | ITT  |
| Screening-failure            | 
Exclusion criteria given prior to screening / enrolment:
 
Patient will be recorded at screening list, but will not be provided with a patient number.
   | -  |

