## 7.2 Efficacy Parameters

### Primary efficacy endpoint:

- Aneurysm rupture (i.e. aneurysmal subarachnoid hemorrhage, SAH) or growth (increase in any aneurysm diameter by  $\geq 1\text{mm}$ ) on serial imaging (either two MR or CT angiographies) within 36 +/- 6 months from randomization.

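### Section 6 keeps every patient on intervention after the primary endpoint, rupture included, while section 4.6.1 ends treatment after rupture in a patient with one aneurysm

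*Protocol*

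**What the plan says.** Four places in the protocol bear on what happens after a rupture or a repair.

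- **Section 6**, on the study period of an individual patient: "all patients stay on intervention until 3 years of the last patients' enrolment, even if the primary endpoint has occurred". The sentence gives the secondary endpoint analyses as its reason. Section 6.3 points the same way: patients are to be asked to continue treatment to month 120 or study end, with no exception for rupture.
- **Section 7.2** defines the primary endpoint as "Aneurysm rupture (i.e. aneurysmal subarachnoid hemorrhage, SAH) or growth" within 36 ± 6 months of randomisation.
- **Section 4.6.1**, under disease progression: "In patients with 1 intracranial aneurysm, end of treatment applies if aneurysm rupture (SAH) occurs". The same sentence applies this to endovascular or neurosurgical treatment of that aneurysm. The next sentence reads: "Patients who have multiple aneurysms can stay in the trial if growth, rupture or preventive treatment of 1 aneurysm occurs".
- **Section 5.4.5 A** allows ASA to be interrupted for surgery and has it restarted promptly afterwards. It does not set aneurysm surgery apart.

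On side effects, section 4.6.1 introduces its list with "Reasons leading to the withdrawal of a patient can include the following". One example, under events intolerable on both parts of the intervention, is "Any bleeding that results in hospital inpatient treatment". Later in 4.6.1, for harm from one part only, "it can be decided to adjust or stop the component of the intervention causing the side effects" while the other part continues. Section 5.4.5 B rules out changes to the ASA dose, and the section closes with "No further adjustments are planned".

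**The concern.** A site whose patient has had an SAH needs one answer on whether the study drug goes on. Section 6 answers for all patients and addresses the time after the endpoint explicitly. Section 4.6.1 gives the opposite answer for a named event in a named group. Sites that read different sections would treat the same patient differently, and each could cite the protocol.

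Safety comes first, because the drug is an antiplatelet agent and the event is an intracranial bleed. There is also a smaller analytic effect. Section 6 keeps patients on intervention in order to collect secondary endpoints, so exposure after the first event would depend on which passage a site follows.

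**Working it through.** The check is mainly a comparison of text, taken event by event for an intervention-group patient.

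1. **One aneurysm, rupture within the primary window.** SAH is a primary endpoint event (7.2), so section 6 says continue. Section 4.6.1 says treatment ends. Both apply, and neither cites the other. *Direct contradiction.*
2. **One aneurysm, repaired.** Section 4.6.1 ends treatment. Section 5.4.5 A restarts ASA after surgery. For neurosurgical repair the two collide even if no primary endpoint event has occurred. For endovascular repair it depends on whether a site counts the procedure as surgery. *Related contradiction.*
3. **One aneurysm, growth without repair.** Section 6 says continue, and 4.6.1 names no stop for growth. *No conflict.*
4. **Multiple aneurysms, with growth, rupture or repair of one.** Section 6 says continue, and 4.6.1 permits staying in the trial. The second is weaker but compatible. *No conflict.*
5. **Bleed needing admission.** Both parts of 4.6.1 are permissive. If both components are to blame, withdrawal is possible; if one is, that component can be adjusted or stopped. Bleeding and severe orthostatic hypotension appear as examples in both parts. *Overlap, not opposition.*
6. **Adjusting a component.** If the component is ASA, the verb in 4.6.1 does not fit the bar on dose changes in 5.4.5 B. *Minor inconsistency.*

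**Size.** The protocol gives no count for this. Inputs:

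- 776 patients randomised 1:1 (sections 4.1 and 5.5.1), so 776 / 2 = 388 in the intervention arm.
- 5-year rupture risk usually below 3% in these patients (sections 1.3 and 3.1), used as a ceiling.
- 0.5% as a low value, the bottom of the 5-year range in section 1.1.
- Assumptions: constant hazard and no treatment effect.

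Expected ruptures in 3 years = 388 × [1 − (1 − r)^(3/5)], where r is the 5-year risk:

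- r = 3%: 7.0 (linear version: 388 × 0.03 × 3/5 = 7.0)
- r = 2%: 4.7
- r = 1%: 2.3
- r = 0.5%: 1.2

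The constant hazard is not critical to the conclusion. If the whole 3% fell within the first three years, the count would be 388 × 0.03 = 11.6.

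Only patients with one aneurysm meet the rupture contradiction. The protocol does not give their share, so the affected number is an unknown fraction of about 1 to 7. It gives no repair rate either, so item 2 cannot be sized.

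**The case against.** The strongest reply is that the specific rule governs the general one. Section 6 speaks in parentheses, in a sentence about study duration. Read literally, it would also override the right to withdraw at any time. Section 4.6.1 is the dedicated withdrawal section and names the exact event, so most sites would probably follow it. This has some force as a forecast of behaviour, but it does not settle the text. The section 6 wording addresses precisely the time after the endpoint, gives its reason and covers all patients. The permissive opening of the 4.6.1 list does not help, because the rupture sentence itself is not permissive.

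The other side is right about several stronger readings that a reader might infer:

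- **That a hospitalised bleed means withdrawal in one place and stopping only ASA in another.** Neither is mandatory. The list says "Reasons leading to the withdrawal of a patient can include the following" and the later text says "it can be decided to adjust or stop the component of the intervention causing the side effects", so the two can be read together.
- **That a ruptured aneurysm in a multiple-aneurysm patient is also a listed bleed, so 4.6.1 contradicts itself.** Being allowed to stay and being eligible for withdrawal are compatible. Rupture also has its own entry, apart from the side-effect examples.
- **That section 5.4.5 forbids stopping ASA for side effects.** Section 1.3 lets the treating physician halt ASA, and "No further adjustments are planned" sits in a section on dosage. Only the verb in 4.6.1 is loose.
- **That all patients reaching the primary endpoint are affected, 388 × 8.25% = 32 in the intervention arm.** Growth is the commoner event (section 3.1), and without repair it creates no conflict.
- **That about 23 ruptures over ten years are at stake (388 × 6% = 23.3).** This gives everyone ten years. Section 3.2 has the last patient entering in Q2 2026 and the last leaving in Q2 2029, so late entrants have about three. Ruptures after the 36 ± 6 month window are not primary endpoint events either.

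**Conclusion.** The contradiction between sections 6 and 4.6.1 is real as written for a one-aneurysm patient whose aneurysm ruptures. Section 5.4.5 A adds a related one for surgical repair of a single aneurysm. The rupture group is the one-aneurysm subset of at most about 7 of 388 intervention patients over 3 years. That figure rests on the under-3% five-year risk as a ceiling, a constant hazard and no treatment effect.

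The number is small, but each case is an instruction about an antiplatelet drug after an intracranial bleed or an aneurysm operation, so the text should be corrected. A reader might conclude that the secondary comparisons become uninterpretable. The documents do not support that: stopping treatment after a primary event cannot change that event, the primary analysis is by intention to treat, randomisation is stratified by centre, and few patients are involved. The overlapping side-effect examples and the loose verb are matters of clarity only.

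**What to change.** The investigators and the DSMB should reconcile sections 6, 4.6.1 and 5.4.5 A. One rule should state, after rupture and after repair, and for one or several aneurysms, what happens to the study drug and to trial participation. Place it once and cross-reference it from the other two sections. Which passage gives way is the sponsor's clinical decision.

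Two clarifications belong in the same amendment:

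- In 4.6.1, separate the examples that now appear under both the two-component and the one-component text: hospitalised or major bleeding, and severe orthostatic hypotension.
- Align the wording on adjusting a component in 4.6.1 with the bar on ASA dose changes in 5.4.5 B.

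The cost is one protocol amendment and a letter to sites. No procedures or patients are added, and the sample size and primary analysis are unaffected.
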